Official Title: To Understand the Impact of Immunosuppression Using Once-perday Envarsus XR on the Effect of Total Tacrolimus Dose/Trough Level Ratio on Renal Function (eGFR) in Kidney Transplantation

Unique Protocol ID: AAAR6805

Registration Identifier: NCT03511560

Document Date: June 11, 2019

Primary Objective: To compare the relationship of once daily tacrolimus extended release (Envarsus) versus twice daily tacrolimus immediate release (Prograf) doses to achieve target trough concentrations (C) relative to the total daily dose (D) given and the effect of C/D ratio on renal function at day 7 and months 1, 3, 6, and 12 months after transplantation utilizing concentration to dose ratio (C/D ratio).

Secondary Objective:

- Compare incidence of rejection between the groups at 90 and 365 days post-transplant (Banff grade I-III and antibody mediated rejection [AMR])
- Compare graft loss and death within 1 year post-transplant
- Death within 1 year post-transplant
- Compare and summarize serious adverse events (AEs) between study groups

Study Population: Living or deceased donor kidney transplant recipients 18 to 80 years of age.

Number of Subjects to be Enrolled / Randomized: 50 patients [25 patients in each arm]

Study Design Overview:

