This is a one year, prospective, randomized, open-label trial examining once versus twice daily tacrolimus dosing regimen using two preparations, Envarsus vs Prograf. It will examine kidney function between the two groups using eGFR and also examine one year kidney outcomes, including graft loss and patient death. Biopsy will be performed on clinical indications only (not protocol) when rejection or other problem is suspected in face of deteriorating renal function in each study group utilizing Banff criteria. Patients will be screened prior to surgery and randomized 1:1 to receive, within 48 hours of transplantation, immediate release tacrolimus, administered twice daily, or Envarsus, administered once daily as a component of a standard immunosuppression maintenance regimen also consisting of mycophenolate sodium (MPA) (or mycophenolate mofetil equivalent). Induction therapy will be given and administered per center protocol (rabbit anti-thymocyte globulin 6mg/kg over 4 days except in HLA identical living donor/recipient pairs when basiliximab induction is used intraoperatively). Intravenous corticosteroids (methylprednisolone 500mg intraoperatively with a daily rapid taper to 250, 125, 80 mg) over 4 days will be administered prior to rabbit antithymocyte globulin and prior to revascularization as part of the initial induction regimen. Thereafter, patients will be followed for up to 1 year during the open label study period. After discharge from the hospital, the patients randomized to immediate-release tacrolimus will be permitted to receive any immediate release tacrolimus product available to them through normal dispensing mechanisms. Envarsus will be supplied by Veloxis and dispensed by the research pharmacy.

Inclusion Criteria:

Subject is eligible for the study if all of the following apply:

1. Kidney transplant patient \ge 18 years and \le 80 years old

- 2. Institutional Review Board (IRB) approved written Informed Consent and privacy language must be obtained from the subject prior to any study-related procedures (including withdrawal of prohibited medication, if applicable).
- 3. Recipient of a *de novo* kidney from a living or deceased donor.
 - a. If deceased donor, a Kidney Donor Profile Index (KDPI) ≤ 85% are eligible for enrollment.
- 4. Willingness to comply with study protocol.

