Endpoints for Evaluation:

Primary: To compare the relationship of once daily tacrolimus extended release (Envarsus) versus twice daily tacrolimus immediate release (Prograf) doses to achieve target trough concentrations (C) relative to the total daily dose (D) given

and the effect of C/D ratio on renal function at day 7 and months 1, 3, 6, and 12 months after transplantation utilizing concentration to dose ratio (C/D ratio).

Secondary: Comparison between treatment cohorts regarding incidence will rely upon assessments for each of the following results:

- Compare incidence of rejection between the groups at 90 and 365 days post-transplant (Banff grade I-III and antibody mediated rejection [AMR])
- Compare graft loss and death within 1 year post-transplant
- Compare and summarize serious adverse events (AEs) between study groups
- Death within 1 year post-transplant

Statistical Analysis:

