Sample Size: The sample size for this pilot study is not sufficiently powered to document that the C/D ratio in each patient group will correlate directly with eGFR. We expect to see a trend suggestive that the Envarsus group by virtue of more stable Tacrolimus level and greater compliance over time will be less likely to develop calcineurin-induced nephrotoxicity and therefore result in a better e-GFR. This is not likely to be statistically significant in this inadequately powered study since the variability in donor organs themselves, as well as many other variables, will not permit a precise analysis in this small study sample. However, stratification for living donors and deceased donors may provide important trends in this pilot project which may then guide us to expand the study in more restricted categories of renal allograft recipients. The statistical summary and analysis of safety data, will consist of all subjects who enrolled into the study and took at least one dose of study medication. Demographics and other baseline characteristics will be summarized by treatment group. Descriptive statistics (e.g., n, mean, standard deviation, minimum, median, maximum) and interquartile range, coefficient of variation, and geometric mean will be provided for tacrolimus dose and whole blood concentrations of tacrolimus for both study cohorts. Tacrolimus concentrations will be summarized with descriptive statistics. The analysis of efficacy regarding C/D effectiveness in relation to number of rejection episodes and outcomes at various stated time points will be conducted using Student T test. The association between whole blood concentrations and the following endpoints will be assessed: rejection episode and eGFR, histopathology (Banff classification) and conventional measures of transplant outcomes.

H0: The probability of incidence for the primary endpoint is the same between patients receiving Envarsus and patients receiving immediate-release tacrolimus.

Safety: All adverse events (AE) will be listed. The number and percentage of AEs, significant AEs, AEs leading to discontinuation, and AEs related to study drug will be summarized by treatment group. The number and percentage of AEs by severity will also be summarized.

Randomization will be performed in excel prior to initiation: Allocation will consist of a 1:1 ratio for twice daily, immediate-release tacrolimus or Envarsus.

Institutional Review Board (IRB)

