Version Date: 11Jun2019 8 of 16 populations (race, sex, age, and diabetes) should provide evidence for possible greater efficiency and lesser toxicity of extended release drug, Envarsus, as compared to SOC treatment with immediate release tacrolimus given twice per day. Envarsus is an oral, extended-release formulation of tacrolimus developed to enable a once daily dosing regimen. It decreases intra-patient variability and offers flatter kinetics which should ensure a more consistent immunosuppression exposure over the long-term without unpredictable high peaks which may be related to higher toxicity rate, including nephrotoxicity. There is little doubt that the once daily dosing has been described as improving medication adherence [Sabbatini et al, 2014; Doesch et al, 2013; Eberlin et al, 2013; Kuypers et al, 2013].

Since Tacrolimus, the mainstay of immunosuppression in renal transplant patients is known for drug induced nephrotoxicity, which may limit graft survival we propose a prospective randomized study to analyze the relationship of tacrolimus doses to achieve target trough levels (C/D) and renal function at different time-points after transplantation. In this analysis, all 1:1 randomized renal allograft recipients maintained with mycophenolate sodium will be treated either with tacrolimus (Prograf) in the SOC treated controls or with Envarsus in the experimental group. Renal function will be estimated by MDRD equation (eGFR MDRD). Such a prospective, randomized, controlled pilot trial to compare the use of once a day Tacrolimus (Envarsus) vs. twice a day Tacrolimus (Prograf) to test the hypothesis that the consistency of immunosuppression with Envarsus increases the C/D ratio, i.e. get effective stable trough levels with lower total Tacrolimus dose given as Envarsus, and lead to better eGFR, and reduce the likelihood of nephrotoxicity (lower total Tacrolimus exposure). In the course of this study, patients in the control arm will receive immediate-release formulations of tacrolimus in accordance with local SOC dispensing practices, thus preserving the real-world conditions in which the patient could receive any manufacturer's approved product. In this manner, it is hoped that this research will improve the understanding of chronic calcineurin inhibitor injury and provide greater insight into how tacrolimus exposure impacts long term, and even short term, renal function (eGFR).

Pharmacokinetics

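### The between-arm eGFR comparison that the protocol announces and hypothesises is not carried into the endpoint lists or the analysis text; the only eGFR analysis listed is a non-randomised association with C/D or blood concentration.

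*Combined protocol and SAP*

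**What the plan says.** The intention to compare kidney function by arm is in the document:

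- Study Design Overview, of the trial: "It will examine kidney function between the two groups using eGFR".
- Background: the hypothesis is that Envarsus will raise C/D "and lead to better eGFR, and reduce the likelihood of nephrotoxicity (lower total Tacrolimus exposure".
- Statistical Analysis, Sample Size: a trend is expected in which the Envarsus group "will be less likely to develop calcineurin-induced nephrotoxicity and therefore result in a better e-GFR".
- Efficacy Assessment: MDRD eGFR is calculated at day 7 and months 1, 3, 6 and 12.

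The endpoint lists say something else. The Primary Objective and the primary entry under Endpoints for Evaluation have two parts: the C/D comparison between formulations, "and the effect of C/D ratio on renal function at day 7 and months 1, 3, 6, and 12 months after transplantation". The secondary endpoints open with "Comparison between treatment cohorts regarding incidence will rely upon assessments for each of the following results" and then name rejection, graft loss and death, death alone, and serious adverse events. eGFR by arm is in neither list.

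**The concern.** The stated hypothesis is about the assigned treatment. The listed renal analysis is about a quantity observed after assignment. These are different questions, and only the first is protected by randomisation.

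Two errors become possible if the listed association is taken as the trial's renal result. C/D and eGFR may be related through patient characteristics when Envarsus has no effect on eGFR. Conversely, a real effect of Envarsus that does not act through C/D may leave no trace in the association. The second case matters here because the Sample Size paragraph attributes the expected benefit to steadier levels and better adherence, neither of which C/D need capture.

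**Working it through.** **1. Is there an analysis of eGFR by arm?** The Statistical Analysis section, taken item by item:

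- Descriptive statistics are specified for tacrolimus dose and blood concentration, not for eGFR.
- The Student t test is assigned to how C/D relates to rejection counts and to outcomes over time, not to eGFR by arm.
- eGFR is named as an outcome only in an association with whole blood concentration.
- The null hypothesis does compare the arms, but on an incidence probability, which fits neither eGFR nor C/D.

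No item gives the eGFR contrast a time point, a summary measure or a test.

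**2. Can C/D stand in for the arm?** The Background presents C/D as an expression of metabolism rate, so it varies between patients within an arm as well as between formulations. Randomisation balances the arms; it does not balance patients with high and low C/D. The Treatments and Pharmacokinetics sections add that equal trough targets give equal systemic exposure with either product. A C/D difference between arms may then largely reflect dose, and need not bring an eGFR difference with it. Comparing the C/D-eGFR relationship between arms would compare slopes, which is again not the eGFR difference.

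**3. The sample size.** The document gives 50 patients, 25 per arm, with no alpha, power, effect size or SD. Beyond 25 + 25 = 50 there is nothing to reproduce.

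**4. Precision of the missing comparison.** All SDs are assumptions (mL/min/1.73 m²), and all 25 patients per arm are taken to contribute a value.

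95% CI half-width = t(0.975, 48) × SD × √(2/25) = 2.011 × SD × 0.2828

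- SD 15: 8.5
- SD 18: 10.2
- SD 20: 11.4

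Difference detectable with 80% power, two-sided 0.05 = (1.960 + 0.842) × SD × √(2/25)

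- SD 15: 11.9
- SD 20: 15.9

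**5. Illustration of how the two questions can part.** 20,000 simulated trials per scenario, 25 per arm, eGFR SD 18, SD of log C/D 0.45, all assumed.

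(a) No Envarsus effect on eGFR; C/D 30% higher on Envarsus (ln 1.3 / 0.45 = 0.58 SD); within-arm correlation of C/D and eGFR 0.3 or 0.4, arising from patient factors:

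| Test | Correlation 0.3 | Correlation 0.4 |
|---|---|---|
| C/D-eGFR, both arms pooled | 54% significant | 80% significant |
| C/D-eGFR, one arm (n = 25) | 31% | 53% |
| eGFR by arm, t test | 5% | 5% |

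(b) True Envarsus benefit of 8 mL/min not acting through C/D: the pooled association is significant in 5% to 7% of trials. The arm t test is significant in about 34%, with an unbiased mean estimate of 8.0.

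The association figures in (a) are essentially the power to detect the correlation that was put in. They show that the two analyses answer different questions; they do not estimate an error rate of this trial.

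**The case against.** The strongest reply has four parts.

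*The comparison is in the protocol.* This stands. A reader might infer from the endpoint lists that an eGFR comparison by arm was never intended. The Study Design Overview says otherwise, and eGFR heads the Efficacy Assessment section. The gap concerns endpoint status and analysis, not intent.

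*The C/D-eGFR question is a declared aim.* This also stands. The trial's title is about the dose/trough ratio and renal function, the Background proposes to study the impact of C/D on kidney function in both groups, and the Study Design section calls the trial an exploratory pilot. Such a primary question is legitimate. It does not, however, answer the Background's other hypothesis, that Envarsus leads to better eGFR.

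*The protocol disclaims a firm result.* It says that "sample size for this pilot study is not sufficiently powered to document that the C/D ratio in each patient group will correlate directly with eGFR" and, of the expected eGFR trend, "This is not likely to be statistically significant in this inadequately powered study". A reader might infer that a significant C/D-eGFR association would be declared an Envarsus benefit. No success rule is attached to that association and no section says it would be read so. But low power is a reason to report an estimate with its interval, not to leave the comparison off the list. The estimate is also useful for the expanded study that the pilot is meant to guide.

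*The simulation tests something the plan does not name.* Correct. No pooled correlation is specified, and the Sample Size wording points to analysis within each group, where the percentages are much lower. The arm comparison is itself weak, detecting 8 mL/min in only about a third of trials at SD 18.

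**Conclusion.** The point holds as an inconsistency between what the protocol announces and what it lists and analyses. It rests on the text and on the status of C/D as a post-randomisation variable, and needs no simulation. As written, the only listed analysis of eGFR cannot by itself show whether Envarsus improves it.

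The documents do not support the stronger reading that the primary endpoint is invalid, nor a demand that between-arm eGFR be co-primary. With 25 per arm, only differences of roughly 12 to 16 mL/min/1.73 m² would be detected with 80% power at an assumed SD of 15 to 20. A first secondary endpoint reported by estimation is what the sample can carry. The half-width of 8.5 to 11.4 depends on those SDs and on complete data; missing values would widen it. The simulated percentages are illustrative only.

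**What to change.** In the synopsis objectives and in Endpoints for Evaluation, add as the first secondary endpoint: the difference between arms in MDRD eGFR at month 12, by randomised arm, as an estimate with 95% confidence interval, with the other eGFR time points supportive. Add a matching sentence to Statistical Analysis.

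State that any conclusion about Envarsus and renal function rests on this comparison. Keep the C/D-eGFR association as a declared aim, report it within each arm, and label it non-randomised and exploratory.

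The cost is wording only, since eGFR at month 12 is already planned. The downside is that a wide interval will be shown openly.

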This is an exploratory, pilot one year, prospective, randomized, open-label trial examining long-term kidney transplant outcomes. Specifically, it is designed to compare the effects of twice daily, immediate-release tacrolimus and once daily Envarsus on trough Tacrolimus concentrations (C) relative to the total daily dose (D) given and to determine the effect of C/D ratio on renal function at day 7 and months 1, 3, 6, and 12 months after transplantation utilizing concentration to dose ratio (C/D ratio). Patients will be screened prior to surgery and randomized 1:1 to receive, within 48 hours of transplantation, immediate-release tacrolimus, administered twice daily, or Envarsus once daily, as a component of a standard immunosuppression maintenance regimen also consisting of peri-transplant only corticosteroids and mycophenolate sodium (MPA), or equivalent. Induction therapy will be given and administered per center protocol. Intravenous corticosteroids will be administered prior to revascularization as part of the initial induction regimen, with dose and duration of therapy also determined by the standard protocol which tapers steroids off within 5 days of transplantation with few exceptions (patients who have been maintained on steroids prior to transplant and patients with IGA nephropathy). Thereafter, patients will be followed for up to 1 year during the open-label study period. Immediaterelease tacrolimus will be obtained from pharmacies per the local standard of care. After discharge from the hospital, the patients randomized to immediate-release tacrolimus will be permitted to receive any immediate-release tacrolimus product available to them through normal dispensing mechanisms. Envarsus will be supplied by Veloxis and dispensed by the Research Pharmacy. Additionally, all local kidney biopsy results, local laboratory results, AEs, and concomitant medications pertaining to AEs will be recorded. At the terminal study visit at 12 months, the most recently obtained lab results as well as any episodes of rejection, graft loss, and deaths occurring beyond the first year will be detailed and reported to the IRB. Pathology results [hematoxylin and eosin (H&E), light microscopy, and immunofluorescence] will be recorded when local kidney biopsies are performed and interpreted during the course of clinical care. Substantiation by local biopsy will be required for cases of suspected rejection. A kidney biopsy will be graded by the most recent version of the 2007 Update to the Banff '97 Classification by our renal pathologist blinded to clinical results.

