
Version Date: 11Jun2019 10 of 16

Study Visits

Screening Period

The screening period can be any time from 21 days before your transplant until the day of transplant. At the screening visit, the following procedures and tests will be performed:

-A review of current health status, medical and surgical history, and list of medications

-Collection of blood samples for clinical purposes.

-A physical examination (including height and weight)

- Questions about any side effects that may occur from the medications taken.

-Female participants who are able to have children will also have a pregnancy test (either from a blood draw or a urine sample) within the 14 days before the kidney transplant as per standard-of-care.

For deceased donor, the screening and randomization procedures may take place on the day of transplant.

For living donors, randomization procedures may take place on the day of transplant.

Randomization

Subjects will be randomized to two open label treatment arms in a 1:1 ratio by a computer program. The two treatment arms are: Treatment Arm 1: Study medication is once daily Envarsus, or slow-release tacrolimus; Treatment Arm 2: Study medication is twice daily, Prograf, or immediate-release tacrolimus. Randomization will happen the day of transplant to ensure all questions have been answered prior to surgery and the subject wishes to remain in the study.

Subjects randomized to Envarsus will need to take the study medication once a day at the same time each day, by mouth. For both treatment arms, the medications that you take in preparation for your kidney transplant ("induction therapy") and the other medications that the study medication needs to be taken with (including steroids and mycophenolate mofetil [MMF]) will be given to you in the way your doctor normally gives them. These medicines will not be paid for or reimbursed by the study sponsor because they need to be taken whether or not you are in the study. ONLY the study medication Envarsus will be provided to you by the sponsor for no charge.

Follow Ups

Both Arms of the study will have the same 11 planned study visits to the research center, which will be done monthly post-transplant until the 1 year follow up is completed. When possible, all visits will be done in conjunction with standard-of-care-follow up visits with the nephrologist. If the subject is unable to return for an in-person appointment, a phone call visit will be used in its place with the research staff.

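### Donor type and donor age are collected but no stated allocation or analysis uses them; prespecifying both as covariates in the between-arm eGFR comparison is a cheap step with a conditional gain

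*Combined protocol and SAP*

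**What the plan says.** The Sample Size paragraph under Statistical Analysis warns that "the variability in donor organs themselves, as well as many other variables, will not permit a precise analysis in this small study sample". It follows this with the hope that "stratification for living donors and deceased donors may provide important trends in this pilot project", which might guide a later study in narrower groups of recipients. Nothing further is said about stratification.

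Allocation is described in three places, none with strata. The statistics section says "Randomization will be performed in excel prior to initiation: Allocation will consist of a 1:1 ratio". The Randomization text under Study Visits says "Subjects will be randomized to two open label treatment arms in a 1:1 ratio by a computer program". Footnote 2 to the Schedule of Events uses donor type only to set when randomization takes place.

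Donor type and donor age are both recorded (Data collection, Transplant Information). No model, table or covariate list refers to either.

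The Study Design Overview says of the trial: "It will examine kidney function between the two groups using eGFR". The Sample Size paragraph expects better eGFR on Envarsus. The endpoint lists, however, contain the C/D ratio and its effect on renal function, rejection, graft loss, death and serious adverse events, with no between-arm eGFR difference as such. The only test named is for the effectiveness of C/D in relation to rejection and "outcomes at various stated time points will be conducted using Student T test". eGFR appears in the analysis text only as something to be associated with blood concentrations, with no method attached.

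**The concern.** The plan identifies a source of noise, records baseline data that describe it, and then leaves those data out of every stated analysis. If donor type and donor age explain a useful share of eGFR variance, an unadjusted comparison gives up precision that could be had at no cost in patients or visits. A model chosen after open-label eGFR results have been seen by arm would also carry less weight than one fixed beforehand.

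The donor-type trends are meant to inform the next study, yet the plan does not say how they will be estimated or how wide their intervals would be.

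The point concerns the precision of the between-arm eGFR comparison only. It says nothing about the C/D comparison.

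**Working it through.** **The plan's own figure.** The only figure is 50 patients, 25 per arm. No alpha, power, effect size or SD is stated, so there is no calculation to reproduce.

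**Assumptions, none given in the documents.** Two-sided 5%; 50 evaluable (40 as a sensitivity case); eGFR SD of 15 or 20 mL/min, with 25 as a check; a true difference of 10 mL/min for power; R2, the share of eGFR variance explained by donor type plus donor age, from 0 to 0.3; a 25/25 living/deceased mix where a mix is needed.

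**Unadjusted comparison.** SE = SD x sqrt(2/25): 4.24 at SD 15 and 5.66 at SD 20. The 95% CI half-width is t(48) x SE with t(48) = 2.011: 8.53 and 11.37 mL/min. Noncentral-t power for 10 mL/min is 64% and 41%.

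**Adjusted comparison.** With q covariates the expected variance ratio, adjusted to unadjusted, is (1 - R2) x (N - 3)/(N - q - 3). For N = 50 and q = 2 this is (1 - R2) x 47/45, and the CI uses t(46) = 2.013.

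| R2 | SE ratio | Half-width, SD 15 | Half-width, SD 20 | Power, SD 15 | Power, SD 20 |
|---|---|---|---|---|---|
| unadjusted | 1 | 8.53 | 11.37 | 64% | 41% |
| 0 | 1.022 | 8.73 | 11.64 | 62% | 40% |
| 0.05 | 0.996 | 8.51 | 11.34 | 64% | 41% |
| 0.1 | 0.970 | 8.28 | 11.04 | 66% | 43% |
| 0.2 | 0.914 | 7.81 | 10.41 | 71% | 47% |
| 0.3 | 0.855 | 7.30 | 9.74 | 77% | 53% |

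Break-even is at 1 - R2 = 45/47, so R2 = 2/47 = 0.043. At R2 = 0.3 the equivalent unadjusted sample is 50/0.731 = 68. At SD 25, power goes from 28% unadjusted to 37% at R2 = 0.3.

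**40 evaluable.** The factor is 37/35. SE ratios are 1.028, 1.002, 0.975, 0.920 and 0.860 for the same R2 values; break-even is 2/37 = 0.054.

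**Donor type alone (q = 1, 25/25 mix).** R2 = 0.25 x gap^2/SD^2, where gap is an assumed living-deceased difference in mean eGFR. SE ratios at SD 15 and SD 20 are 0.997 and 1.003 (gap 5), 0.953 and 0.979 (gap 10), 0.875 and 0.937 (gap 15). The gain runs from nil to modest.

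**Donor-type results.** With 12.5 per arm in each stratum, the half-width of the treatment difference within a stratum is t(23) x sqrt(2/12.5) = 0.83 within-stratum SD. If that SD is also taken as 15 to 20, this is 12 to 17 mL/min. For the treatment-by-donor-type interaction it is t(46) x sqrt(2/12.5 + 2/12.5) = 1.14 SD. At a 15/35 mix the within-stratum figures are 1.12 and 0.69 SD, and the interaction is 1.24 SD.

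**The case against.** The strongest reply is that the plan already concedes the point. It states that "This is an exploratory, pilot one year, prospective, randomized, open-label trial", calls itself inadequately powered, names donor variability and expects no significant result. The comparison at issue is not a listed endpoint, and no conclusion from the pilot is shown to change. All of that stands. It limits how much weight the point can bear, but it is no reason to leave collected baseline data unused.

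A second reply is that the benefit is unproven. That also stands. R2 is unknown and may differ between day 7 and month 12. The cap in the eligibility criteria ("If deceased donor, a Kidney Donor Profile Index (KDPI) ≤ 85% are eligible for enrollment") may narrow donor variation and lower R2. The low rows of the table deserve as much attention as the high ones.

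A third is that the covariates are a matter of preference, since ischemia time and HLA mismatch are recorded too. In part this is so. Donor type is the factor the plan itself singles out. Donor age is a judgement, and with 50 patients the list should stay short.

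A reader might infer three stronger things that the documents do not support:
- **That stratified randomization was promised and then dropped.** The single sentence fits equally well with a descriptive analysis by donor type, so the accurate word is unspecified.
- **That unstratified 1:1 allocation biases the comparison.** It is valid and unbiased on average.
- **That the plan has no method at all for eGFR.** The t test's reference to outcomes can be read to include it; it is simply not clearly tied to it.

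**Conclusion.** The point holds as a weakness of specification with a possible cost in precision. The plan names donor variability as a problem and leaves its stratification remark undefined, and no stated allocation or analysis uses the donor type and donor age it collects. Under the assumptions listed, adjusting for both changes the standard error by between +2% and -14% for R2 from 0 to 0.3. The possible loss is small and bounded, and the possible gain is several times larger but conditional on an R2 the documents do not give.

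Adjustment does not rescue the trial's power, and a reader should not take it to. For 10 mL/min at SD 20 the best case shown is 53%. Donor-type results will be wide under any analysis. Confidence in the textual finding is high; confidence in the size of the gain is moderate at most.

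**What to change.** 1. State whether stratification refers to allocation, analysis or subgroup description.
2. Prespecify the between-arm eGFR comparison as a linear model at day 7 and months 1, 3, 6 and 12, with arm, donor type and donor age, and report the unadjusted difference beside it. Leave KDPI out, because the eligibility criteria apply it only to deceased donors. Do this as early as possible and before any comparison of eGFR by arm. Waiting for the 6-month interim analysis described under Formal Stopping Rules would be late, because treatment is open-label and eGFR up to month 6 would already be on record.
3. Report donor-type results as exploratory estimates with 95% CIs.
4. In the same addition, say which time point leads and how missing eGFR after graft loss or death is handled. The model alone does not settle either.

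The cost is a short addition to the analysis section and two degrees of freedom. If the covariates explain nothing, the standard error is about 2% larger (3% with 40 evaluable), and power for 10 mL/min at SD 20 falls from 41% to 40%. No extra data, visits or patients are needed.
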